## **7.5 Analysis of Safety**

[Analysis population: SAF, Analysis group: Randomization Arm and Total]

### **7.5.1 Adverse Events**

Summaries and listings of serious adverse events (SAEs) and Serious TEAEs include SAEs upgraded by the sponsor based on review of the Sponsor's list of Always Serious terms if any upgrade was done.

The coding dictionary for this study will be MedDRA. It will be used to summarize AEs by system organ class (SOC) and preferred term (PT).

An overview table will include the following details:

- Number of TEAEs,
- Number and percentage of subjects with TEAEs,
- Number of drug related TEAEs,

- Number and percentage of subjects with drug related TEAEs,
- Number of serious TEAEs,
- Number and percentage of subjects with serious TEAEs,
- Number of serious drug related TEAEs,
- Number and percentage of subjects with serious drug related TEAEs,
- Number of TEAEs leading to death,
- Number and percentage of subjects with TEAEs leading to death,
- Number of TEAEs leading to withdrawal of treatment,
- Number and percentage of subjects with TEAEs leading to withdrawal of treatment,
- Number of drug related TEAEs leading to withdrawal of treatment,
- Number and percentage of subjects with drug related TEAEs leading to withdrawal of treatment, and
- Number of deaths.

The number and percentage of subjects with TEAEs, as classified by SOC and PT will be summarized for each treatment group. Summaries will be provided for:

- TEAEs
- Drug related TEAEs,
- serious TEAEs,
- Drug related serious TEAEs,
- TEAEs leading to death,
- Drug related TEAEs leading to death,
- TEAEs leading to withdrawal of treatment,
- Drug related TEAEs leading to withdrawal of treatment,
- TEAEs excluding serious adverse events that equal to or exceed a threshold of 5.0% in any treatment group,
- Frequently reported TEAEs that equal to or exceed a threshold of 5.0% in any treatment group, and
- Frequently reported drug related TEAEs that equal to or exceed a threshold of 5.0% in any treatment group.

The number and percentage of participants with TEAEs, as classified by PT only, will be summarized for each treatment group.

The number of TEAEs and the number and percentage of subjects with TEAEs, as classified by SOC and PT will also be summarized by severity using National Cancer Institute-Common Terminology Criteria for Adverse Events (NCI-CTCAE). In the subject count, if a subject has multiple TEAEs with the same SOC or PT, but with differing NCI-CTCAE Grade, then the subject will be counted only once with the worst NCI-CTCAE Grade, however, if any of the NCI-CTCAE Grade values are missing then the subject will be counted only once with missing NCI-CTCAE Grade. In the adverse event count, the adverse events will be presented in each category they were classified to. Drug related TEAEs will be presented in a similar way by NCI-CTCAE Grade.

The number and percentage of subjects with TEAEs, as classified by SOC and PT will be summarized for each treatment group by time interval. For each adverse event in a particular interval, a subject will be counted if there is an onset of a treatment-emergent adverse event regardless of onset in other intervals.

Time intervals will be categorized according to the following categories:

- $\geq 0$  hours to  $\leq 24$  hours after T0
- $> 24$  hours to  $\leq 48$  hours after T0
- $> 48$  hours to  $\leq 72$  hours after T0
- $> 72$  hours after T0 to  $\leq$  Day 7 or DoD
- $>$  Day 7 or DoD to  $\leq$  Day 30

The number and percentage of subjects with TEAEs, as classified by SOC and PT will be summarized for each treatment group by subgroups defined in [Section 7.8].

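### In the subject count of the severity tables, one missing CTCAE grade overrides a recorded Grade 3-5 in the same SOC or PT, so the number of subjects with severe TEAEs can be understated

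*SAP*

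**What the plan says.** SAP 7.5.1 (Adverse Events) sets up a severity table with two kinds of count: "The number of TEAEs and the number and percentage of subjects with TEAEs, as classified by SOC and PT will also be summarized by severity".

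The subject count has a default and an override.

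- Default, for several events in one row whose grades are not all equal: "then the subject will be counted only once with the worst NCI-CTCAE Grade".
- Override: "if any of the NCI-CTCAE Grade values are missing then the subject will be counted only once with missing NCI-CTCAE Grade".

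The event count follows a different rule, given in the next sentence: "In the adverse event count, the adverse events will be presented in each category they were classified to". The scheme carries over to related events: "Drug related TEAEs will be presented in a similar way by NCI-CTCAE Grade".

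The same section also has subject-level outputs that do not depend on the grade, among them "Number and percentage of subjects with serious TEAEs" and "Number and percentage of subjects with TEAEs leading to death". Protocol 7.5.1 asks for a severity summary, says nothing about missing grades, and provides for a listing of every adverse event. No other section of either document reverses or limits the override.

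**The concern.** A recorded grade is known information. If a subject has a Grade 4 event and an ungraded event in the same row, the true worst grade is at least 4. Reporting that subject as missing discards a valid lower bound because a different record is incomplete.

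The rule also points the opposite way from its neighbours. SAP 6.2 treats an event with no causality assessment as drug-related, and SAP 7.5.2.1 uses each subject's highest liver value. In the severity table, an incomplete record lowers the count of severe cases.

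Safety and tolerability is a secondary objective (Protocol 2.1.2), and the severity of adverse events is a listed safety endpoint (Protocol 2.3.4). What is at stake is how many subjects per arm appear at Grade 3 or above in each SOC and PT row. The chance of being moved to missing rises with the number of events a subject has in the row. The loss is therefore likeliest in subjects with the most events, and in whichever arm has more events per subject.

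**Working it through.** **The plan's own figure.** There is none to reproduce. Neither document states a missing-grade rate or the number of events expected per subject in an SOC.

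**Step 1: apply the rule as written.** The table compares the SAP subject count with a count at the worst recorded grade, where the missing category is used only if every grade is missing.

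| Grades in one SOC or PT row | SAP subject count | Worst recorded grade | Event count (either rule) |
|---|---|---|---|
| 3, missing | missing | 3 | one Grade 3, one missing |
| 5, missing | missing | 5 | one Grade 5, one missing |
| 1, 4, missing | missing | 4 | one each of Grade 1, Grade 4, missing |
| missing only | missing | missing | one missing |
| 2, 3 | 3 | 3 | one Grade 2, one Grade 3 |

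The two subject counts differ only when a row holds at least one recorded and at least one missing grade. The event count never differs.

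**Step 2: which rows are affected.** The rule is applied within an SOC and within a PT. Suppose a subject has a Grade 4 event under one preferred term and an ungraded event under another, both in the same SOC. The PT row for the first term still shows Grade 4, but the SOC row shows missing. SOC rows are therefore the more exposed, since they collect more events per subject.

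**Step 3: how often this could happen.** Inputs, all assumed for illustration:

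- m, the probability that an event's grade is missing, equal across events and independent between them;
- k, the number of events the subject has in the row, one of them a severe event whose grade is recorded.

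Only the other k - 1 events can mask the recorded one, so

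P(masked) = 1 - (1 - m)^(k - 1).

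With k = 5 the exponent is 4:

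- m = 1%: 1 - 0.99^4 = 1 - 0.9606 = 3.9%
- m = 3%: 1 - 0.97^4 = 1 - 0.8853 = 11.5%

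An exponent of 5 would be wrong here. It would include cases where the severe event is itself the ungraded one, and then no known severe grade is lost.

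A wider range:

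| m | k = 2 | k = 3 | k = 5 |
|---|---|---|---|
| 0.5% | 0.5% | 1.0% | 2.0% |
| 1% | 1.0% | 2.0% | 3.9% |
| 2% | 2.0% | 4.0% | 7.8% |
| 5% | 5.0% | 9.8% | 18.6% |

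For every 20 subjects with one recorded Grade 3 or higher event in the row (20 is a round illustrative number), the expected number moved runs from 20 × 0.005 = 0.1 to 20 × 0.1855 = 3.7.

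**The case against.** A reader might infer that the severity table can conceal Grade 3-5 events. The documents do not support that. The sentence after the override keeps each event in its own grade category, so every recorded severe event remains in the event count of the same table. Protocol 7.5.1 words its severity summary in terms of events, and that summary is untouched.

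Nor can a fatal event drop out of the safety report. Serious TEAEs and TEAEs leading to death have subject tables that ignore the grade, including drug-related versions, and all events are listed. Life-threatening events, and those causing or prolonging hospitalisation, are serious by definition (Protocol 5.5.2), which overlaps heavily with the wording for Grades 3 and 4 in Protocol 5.5.4.

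Missing grades may also be rare. Protocol 5.5.4 requires grading, and Protocol 8.1 makes the investigator responsible for complete case report forms, with monitor verification. Finally, an ungraded event has unknown severity, so a missing category avoids presenting the worst recorded grade as though it were the true worst.

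Most of this stands and limits the point to the subject count. Three things remain.

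- Event counts do not give the number or percentage of subjects, because one subject may contribute several events.
- Seriousness and severity are separate classifications, so a Grade 3 event not classed as serious has no other subject-level summary by severity.
- The caution about unknown severity can be met with a footnote. It does not justify discarding a recorded grade, least of all a Grade 5, which no ungraded event could exceed.

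**Conclusion.** The point holds for the subject count only. Following SAP 7.5.1 as written, any missing grade within an SOC or PT moves a subject with a recorded Grade 3-5 event into the missing category. The number and percentage of subjects with severe TEAEs in that row, overall and drug-related, can then be too low. The main exposure is the subject count for non-serious Grade 3 events, especially in SOC rows.

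The size cannot be fixed from the documents. The 3.9% to 11.5% range rests on an assumed 1-3% missing-grade rate, independence between events, and four other events in the row. It applies to subjects with one recorded severe event, not to all subjects. With nearly complete grading it tends to zero. The existence of the problem does not depend on these figures, since it follows from the wording of the rule. It is a minor reporting matter with no bearing on the primary analysis.

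**What to change.** Replace the override in SAP 7.5.1 with a rule of this kind: within each SOC and PT, count the subject at the worst recorded CTCAE grade, and use the missing category only when every grade in that SOC or PT is missing. Apply it to the drug-related table as well. Add a footnote giving the number of subjects with any ungraded event, and state that for them the worst recorded grade is a lower bound.

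The cost is one SAP sentence, one footnote and a small programming change. No new data are needed. The only downside is that lower bound, which the footnote discloses. If few grades are missing, the tables will barely change.

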### **7.5.2 Clinical Laboratory Evaluation**

The baseline visit is the presurgery measurement. In case of missing value at presurgery, the last measurement before surgery will be used as the baseline.

Quantitative clinical laboratory variables, i.e. hematology, biochemistry, and urinalysis will be summarized in SI unit, using mean, standard deviation, minimum, maximum and median for each treatment group at each visit. Additionally, a within-subject change will be calculated as the post-baseline measurement minus the baseline measurement and summarized in the same way. Each laboratory result will be classified as low (L), normal (N), or high (H) at each visit according to the laboratory supplied reference ranges.

Frequency tabulations of qualitative clinical laboratory variables (urinalysis) will be presented for each treatment group at each visit.

For hematology and biochemistry shift table will be presented for each treatment group:

- Summary shifts from of reference range changes from baseline to each visit (shift from normal or high to low, shift from normal or low to high, categorized increase [shift from low to normal or from normal to high], categorized no change [value stays in the same reference range], categorized decrease [shift from high to normal or from normal to low]).

The following data will be presented graphically by treatment group:

- Quantitative Laboratory test results using box plot at each visit.

### 7.5.2.1 Liver Enzymes and Total Bilirubin

The following potentially clinically significant criteria for liver tests – defined as Alkaline Phosphatase (ALP), Alanine Transaminase (ALT), total bilirubin, Aspartate Aminotransferase (AST) and their combination are defined. The subject's highest value after the date of first dosing will be used.

Parameter	Criteria
ALT	> 3x upper limit of normal (ULN) > 5xULN > 10xULN > 20xULN
AST	> 3xULN > 5xULN > 10xULN > 20xULN
ALT or AST	> 3xULN
Total Bilirubin	> 2xULN
ALP	> 1.5xULN
ALT and/or AST AND Total Bilirubin (*)	(ALT and/or AST > 3xULN) and total bilirubin > 2xULN

(\*) Combination of values measured within same sample

The number and percentage of subjects with potentially clinically significant values in liver enzyme and total bilirubin tests during the investigational period will be presented by treatment group.

The following data will be presented graphically by treatment group:

- Matrix scatter plot of maximum liver tests values during the study.

### 7.5.3 Vital Signs

The baseline visit is the presurgery measurement. In case of missing value at presurgery, the last measurement before surgery will be used as the baseline.

Vital signs (systolic blood pressure, diastolic blood pressure, pulse rate, and body temperature) will be summarized using mean, standard deviation, minimum, maximum and median by treatment group and visit. Additionally, a within-subject change will be calculated per visit as the post-baseline measurement minus the baseline measurement and summarized by treatment group and visit.

Following data will be presented graphically by treatment group:

- Vital sign results using box plot at each visit.

## 7.6 Analysis of PK

[Analysis population: PKAS, Analysis group: ASP1128]

If more than and equal to 50% of values are below the quantification limit (BQL) at a given time point, SD and %CV will not be calculated.

### 7.6.1 Plasma Concentrations

Descriptive statistics will be presented for plasma concentration. Individual and mean concentrations of ASP1128 versus time will be plotted. Plasma concentration and sample times data will be listed. Allowable time windows for inclusion in summary statistics are defined as follows.

**Table 11 Blood Sampling for PK for Inclusion in Summary Statistics**

	Sampling Time	Window
Visit 2	Pre-dose	-90 min to 0 min
	EOI	$\pm 5$ min
	2 to 4 hours	$\pm 20$ min
	4 to 12 hours	$\pm 60$ min
Visit 3	EOI	$\pm 5$ min
Visit 4	Pre-dose	-60 min to 0 min
	EOI	$\pm 5$ min

PK: pharmacokinetics; EOI: end of infusion

## 7.7 Analysis of PD

[Analysis population: PDAS, Analysis group: Randomization Arm and Total]

The natural logarithm of gene expression data and its change from baseline will be summarized using mean, standard deviation, coefficient of variation, minimum, maximum and median by treatment group and time points. The data at predose on Visit 2 will be used as baseline.

Following data will be presented graphically by treatment group:

- The natural logarithm of gene expression data using mean (+/- SD) plot.

Additionally, the gene expression data and its fold change from baseline will be summarized using mean, standard deviation, minimum, Q1, median, Q3 and maximum by treatment group and time points. The data at predose on Visit 2 will be used as baseline.

Following data will be presented graphically by treatment group:

- The fold change from baseline of gene expression data using box plot at each visit.

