### **7.6 Analysis of Pharmacokinetics**

All pharmacokinetic summaries will be provided by time points. Descriptive statistics will include n, mean, minimum, median, maximum, SD, coefficient of variation (CV), geometric mean and geometric CV.

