## **7.7 Analysis of Pharmacodynamics**

Descriptive statistics will be used to summarize gene expression data in the PDAS. These endpoints will be summarized graphically.

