## **7 STATISTICAL METHODOLOGY**

### **7.1 General Considerations**

- For continuous variables, descriptive statistics will include the number of subjects (n), mean, standard deviation (SD), median, minimum and maximum. The number of digits to be used for the mean, standard deviation and median will be added one more digit to raw data with rounding off. The minimum and maximum will be presented with the same number of digit(s) as raw data. In addition, for pharmacokinetics (PK) variables, the coefficient of variation (CV) and the geometric mean will also be calculated.

Frequencies and percentages will be displayed for categorical data. Percentages by categories will be based on the number of subjects with no missing data, i.e. will add up to 100%. Frequencies and percentages will be rounded to one decimal place. For time-to-event variables, the number and percentage of subjects with the event using Kaplan-Meier method, the cumulative event rate will be estimated and a plot will be constructed.

- Summaries based on FAS and PPS (e.g. disposition, baseline and efficacy data) will be presented by planned randomization arm, unless specifically stated otherwise. Safety analysis and other summaries based on SAF will be presented by actual treatment received. Analysis of Observational Cohort based on PFAS will be presented by prognostic factor analysis arm.
- All statistical comparisons will be made using two sided tests at the  $\alpha=0.10$  significance level unless specifically stated otherwise. All null hypotheses will be of no treatment difference, all alternative hypotheses will be two-sided, unless specifically stated otherwise.
- All data processing, summarization, and analyses will be performed using SAS® Version 9.4 or higher on Red Hat Enterprise Linux. Specifications for Table, Figures, and Listings can be found in the TLF specifications for this study.
- For continuous variables that are recorded as “ $<X$ ”, “ $\leq X$ ”, “ $>X$ ”, or “ $\geq X$ ”, the value of “ $X$ ” will be used in the calculation of summary statistics if otherwise noted. The original values will be used for the listings.
- MedDRA will be used as the coding dictionary for adverse event and medical history.
- WHODrug Global B3 will be used as the coding dictionary for previous and concomitant medication.
- For the definition of subgroups of interest please refer to [Section [7.8](#)].

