## **7.11 Handling of Missing Data, Outliers, Visit Windows, and Other Information**

### **7.11.1 Missing Data**

See [Section 6.1] for missing value handling of primary and secondary endpoints. Plasma concentrations of ASP1128 below the quantification limit (BQL) will be presented as “<LLOQ” in listings while treated as zero in the analyses. Target gene expression below the

quantification limit will be presented as “<LLOQ” in listings while treated as half of the LLOQ in the pharmacodynamic analyses.

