		
 
• Add the analyses of area under the curve of SCr and S-cystatin-C through 72 hours after T0 (AUCSCr72h and AUCSCysC72h)
 
	To assess the endpoint
		
 
• Clarify the definition of surgery type (lower risk surgery and higher risk surgery)
 
	For clarification
		
 
• Add frequency table of protocol version number at enrollment vs the time of first study drug taken and those subgroups
 
	To assess the impact of the protocol amendment at Ver.2.0
		
 
• Add the analyses of each individual outcomes of MAKE30/90
 
	To assess the endpoint
		
 
• Add the definition of censored subjects for time to AKI-SCr
 
	To deal with censored subjects
		
 
• Add the analyses of mean difference with 90% CI and t-test for APACHE-II, SCr, Cystatin-C, eGFR based on SCr and Cystatin-C, kidney injury molecule-1 (KIM1) and AKIRisk Score
 
	For detailed summarization
		
 
• Add the subgroup analysis of EQ-5D-5L
 
• Add the analysis of mean difference with 90% CI and t-test for EQ-5D-5L
 
	For detailed summarization

Version	Date	Changes	Comment/rationale for change
		

• Add the analysis of TEAE table by PT only

	For summarization
		

• Add summary statistics of coefficient of variation, Q1 and Q3 for the pharmacodynamic variables

	For detailed summarization
		

• Add the following analyses for Observational Cohort: Each stage of AKI-SCr72h and AKI-SCr7d, Each individual outcomes of MAKE30/90, and Association between MAKE30/90 vs AKI-SCr72h, AKI-SCr7d, and AKI-SCr stage 2 or 3

	For detailed summarization
		

• Add the data handling of the visit windows for the pharmacodynamic variables

	To exclude the values out of the visit window from the analysis

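### SAP 7.7 reports a coefficient of variation for log gene expression and its change from baseline, where SD/mean does not measure relative variability

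*SAP*

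**What the plan says.** **Pharmacodynamics.** Protocol 7.7 asks only for descriptive summaries: "Descriptive statistics will be used to summarize gene expression data in the PDAS". It specifies neither a log scale nor a CV. SAP 7.7 adds both: "The natural logarithm of gene expression data and its change from baseline will be summarized using mean, standard deviation, coefficient of variation", together with minimum, maximum and median, by treatment group and time point. The groups include placebo ("Analysis population: PDAS, Analysis group: Randomization Arm and Total"). The CV is a deliberate addition; the version 4.00 entry in SAP 8 reads "Add summary statistics of coefficient of variation, Q1 and Q3 for the pharmacodynamic variables". A second summary in SAP 7.7, on the raw and fold-change scales, lists no CV: "the gene expression data and its fold change from baseline will be summarized using mean, standard deviation, minimum, Q1, median, Q3 and maximum".

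**Pharmacokinetics.** SAP 7.1 says that for PK variables "the coefficient of variation (CV) and the geometric mean will also be calculated". Protocol 7.6 lists "coefficient of variation (CV), geometric mean and geometric CV", and the protocol synopsis also names the geometric CV. SAP 7.11.1 has ASP1128 concentrations below the quantification limit (BQL) flagged "in listings while treated as zero in the analyses". SAP 7.6 suppresses SD and %CV at any time point where at least half the values are BQL. It does not mention the geometric mean. For gene expression, SAP 7.11.1 substitutes half the LLOQ, so ln(0) does not arise there.

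**The concern.** A CV expresses spread relative to a mean, which requires a ratio scale with a true zero. Log expression has no such zero, because its origin is set by the choice of unit. Log change has a zero, but that zero means no change, and an arm can sit near it. The resulting percentage then says more about the unit, or about the closeness of the mean to zero, than about between-subject variability.

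The table has many such cells. Protocol 5.3.3 names seven genes and four sampling times, and SAP 7.7 makes the first predose sample the baseline. That leaves 7 x 3 = 21 ln-change CVs per arm. Two arms with the same spread could show very different percentages.

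The PK tables have a related but narrower fault: a geometric mean cannot absorb a zero.

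**Working it through.** The documents state no figure on this point, so there is none to reproduce. They also give no mean, SD or unit for gene expression. Every mean and SD below is an assumption, used only to show how the statistic behaves.

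**1. CV of ln levels.** Multiplying expression by c adds ln(c) to the mean of the logs and leaves their SD unchanged, so CV = 100 x SD/(mean + ln c).

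- Values 2, 3, 4, 5: mean ln = 1.197, SD = 0.396, CV = 33.1%.
- The same values x 1000: mean ln = 1.197 + 6.908 = 8.105, SD = 0.396, CV = 4.9%.
- Geometric CV = 100 x sqrt(exp(0.396^2) - 1), about 41% in both units.

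With an assumed SD of 0.5 on the log scale (geometric CV 53.3% throughout):

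| Geometric mean, in the chosen unit | CV of ln level |
|---|---|
| 1000 | 7.2% |
| 10 | 21.7% |
| 2 | 72.1% |
| 1.1 | 525% |
| 1 | undefined |
| 0.9 | -475% |
| 0.5 | -72.1% |

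**2. CV of ln change.** Units cancel, and CV = 100/(mean/SD). With an assumed SD of 0.4:

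| Mean ln change | exp(mean) | Planned CV | Geometric CV |
|---|---|---|---|
| 0.02 | 1.02 | 0.4/0.02 = 2000% | 41.7% |
| -0.05 | 0.95 | 0.4/(-0.05) = -800% | 41.7% |
| 0.7 | 2.01 | 0.4/0.7 = 57% | 41.7% |

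The last column is 100 x sqrt(exp(0.4^2) - 1) = 100 x sqrt(0.1735) = 41.7%.

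**3. An arm whose true mean ln change is zero (assumed).** This was simulated 200,000 times for each combination of n and SD. The n of 110 is the planned arm size, and 99 is 110 x 0.9. The CV was negative in half the runs. Its median absolute value was about 1,470% at n = 99 and 1,550% at n = 110. It exceeded 1000% in absolute value with probability 0.68 and 0.70 respectively. Results were practically the same for SDs of 0.3, 0.5 and 0.8. As a check, |CV| is about 100 x sqrt(n)/|Z| with Z standard normal, and the median of |Z| is 0.6745. That gives 100 x 9.95/0.6745 = 1,475% at n = 99.

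**4. PK geometric mean.** It equals exp(mean of ln x), so a single x = 0 makes it zero or not computable and leaves the geometric CV undefined. In one simulated sample (assumed lognormal, median 500, log SD 0.4, n = 99) with one value set to zero, the geometric mean was 0. The geometric mean of the other 98 values was 522. At the first predose sample, taken before any ASP1128, essentially every value should be BQL. There the 50% rule removes SD and %CV but leaves the geometric mean.

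**The case against.** The strongest reply is that nothing is lost. SAP 7.7 puts the SD of ln expression and of ln change beside the CV, by arm and time point. In the second table above that SD would read 0.4 on every row. The geometric CV is a function of that SD alone, and the geometric mean fold change is the exponential of the reported mean. SAP 7.7 also gives SD and quartiles of raw expression and fold change, with plots. This stands. A reader might infer that variability in target engagement becomes unrecoverable, or useless for planning a later trial. The documents do not support that, because the log-scale SD such planning needs is in the table.

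A reader might also infer that the placebo CV is bound to explode. The documents do not say that the placebo mean ln change will be near zero. Baseline is taken after bypass surgery, the last samples follow the third dose, and nothing states that these genes are stable over that interval. For ln levels, values well above 1 in the chosen unit give an ordinary-looking CV that is still unit-dependent.

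The SAP does not write out the CV formula, and SAP 7.1 leaves table details to separate specifications. SD/mean is the plain reading, and nothing in the SAP says that a geometric CV is meant.

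On PK, a reader might infer that the geometric mean fails throughout. Only the first predose sample is near-certain, and a zero there misleads nobody. Elsewhere BQL frequency is not stated. Phase 1 half-lives of 8.75 to 17.4 hours (multiple-dose part, protocol 1.2.2) suggest that it may be uncommon after dosing. Dropping BQL values from the geometric mean is also a convention with its own drawback: it biases the result upward and uses a different denominator from the arithmetic mean.

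None of this makes the CV of ln levels or ln change a valid statistic.

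**Conclusion.** The point holds as a minor correction. SAP 7.7 explicitly requests a statistic that is unit-dependent for ln levels and, for ln change, unbounded and sign-dependent when the mean is near zero. That follows from the algebra and needs no assumption beyond reading CV as SD/mean. The percentages shown are illustrations based on assumed means and SDs, not forecasts for this trial.

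The effect is confined to descriptive PD tables serving an exploratory objective. One column is uninterpretable, and the adjacent SD already carries the information.

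The PK point is secondary. The zero rule conflicts with the required geometric mean wherever a value is BQL, and the 50% rule does not cover that statistic. The absence of the geometric CV from SAP 7.1 is a plain mismatch with protocol 7.6.

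**What to change.** - **SAP 7.7:** delete the CV of ln expression and of ln change. Report the geometric mean fold change, exp(mean ln change), with geometric CV = 100 x sqrt(exp(SD_ln^2) - 1), where SD_ln is the SD of the ln change, by arm and time point. Keep the ln-scale mean and SD.
- **SAP 7.1 and 7.6:** restore the geometric CV listed in protocol 7.6, and extend the 50% BQL rule to the geometric mean and geometric CV.
- **SAP 7.11.1:** state one BQL convention for these two statistics and show the number BQL at each time point. Using quantifiable values only, or not calculating when any value is BQL, would each serve if stated in advance.

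The cost is a few SAP sentences and a formula change in the PD and PK tables. No new data are needed.
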